5.1.2.2 Cognitive, Motor, and Functional Assessments

For subjects treated with dopaminergic therapy for parkinsonism symptoms, CDR-CCB, Alzheimer's Disease Assessment Scale – 13-Item Cognitive Subscale [ADAS-Cog₁₃], Movement Disorder Society's Unified Parkinson's Disease Rating Scale [MDS-UPDRS] [Part III] and Delis–Kaplan Executive Function System (D-KEFS) assessments should be conducted in the practically defined medication “on” state. The “on” state is defined as the individual's best motor function as determined by the investigator or approximately 1 hour after the dose of dopaminergic therapy. Every attempt should be made to conduct these assessments in the “on” state. In the exceptional circumstance that this is not possible, the assessments could be done in the “off” state. The “on/off” state should be confirmed prior to completion of the respective scales listed above. This information will be collected in the eCOA or the eCRF. If any portion of an assessment is done in the “off” state, then that subject should be rated as in the

“off” state for the whole assessment. Subjects NOT on dopaminergic therapy should be recorded as being in the “on” state for the purpose of analysis.

Caregiver’s input will be needed at Visit 2 for the Penn Parkinson Daily Activities Questionnaire-15 (PDAQ-15), Alzheimer’s Disease Cooperative Study – Clinician Global Impression interview, MDS-UPDRS, Neuropsychiatric Inventory (NPI), Epworth Sleepiness Scale (ESS), and Questionnaire for Impulsive-Compulsive Disorders in Parkinson’s Disease (QUIP) scales.

The C-SSRS “Since Last Visit” scale will be assessed. If, based on assessment of the C-SSRS, it is determined that suicide-related behaviors have occurred, then the Lilly Self-Harm Follow-Up form will be used to collect additional information to allow for a more complete assessment of these behaviors.

5.1.2.3 Actigraphy and iPad Device

The actigraphy device, similar to a watch, will be placed on the wrist of the subject at Visit 2 (if available and if consented) for the 2-week period of time until Visit 3 (see Section 9.8.1.2 and the Operations Manual).

An iPad configured with the Lilly Trial application (Lilly Trial app) will be provided to the subjects (if available and if consented) (see Section 9.8.1.1 and the Operations Manual).

Subjects should complete assessments starting the day following Visit 2, throughout the dosing period, and for 2 weeks after the conclusion of the treatment period (until Visit 801). This assessment should be done up to twice daily.

5.1.2.4 Home Blood Pressure Monitoring

The subject should be given the home blood pressure monitoring (HBPM) device at Visit 2 and instructed to measure Home BP twice daily in the seated position using the HBPM equipment provided by Lilly for a minimum of 7 days between Visit 2 and Visit 3. Home BP should be measured twice in the morning (approximately 1 minute apart) (e.g., 8 AM) immediately following study medication dosing and twice in the evening, approximately 12 hours later (approximately 1 minute apart) (e.g., 8 PM).

5.1.3. Double-Blind Period (Visit 3 through Visit 11)

See the Schedule of Activities (Section 2) for the timing of events and the measures to be assessed during the double-blind period.

Estimated length of study visits:

- Visit 3: approximately 8 hours
- Visit 4, Visit 5, Visit 6, Visit 7, Visit 9, and Visit 10: approximately 2 hours
- Visit 8 and Visit 11: approximately 6 hours

All study procedures for the respective visits should be completed within 1 day. In exceptional circumstances, if the clinical assessments cannot be completed within 1 day at V3, V8, and/or V11, those clinical assessments may be completed the next day. The orthostatic blood pressure measurements, in-clinic blood pressure measurements, the CDR-CCB, and the laboratory

procedures including PK must be completed on the first day of that visit. The visit interval will start from the first day of visit.

Visit 3 (Day 1 of dosing)

5.1.3.1. Orthostatic BP/Pulse Rate Measurements

Prior to dosing, orthostatic BP/pulse rate measurements will be collected at time 0 of the in-clinic BP/pulse rate monitoring. Subjects will have 3 BP/pulse rate measurements taken in the seated position approximately 1 minute apart followed by 1 BP/pulse rate measurement taken in the standing position. Subjects should be seated for at least 5 minutes and stand for at least 3 minutes prior to taking the respective measurements. If the subject feels unable to stand, vital signs only in the seated position will be recorded.

The mean should be calculated from the 3 initial in-clinic BP/pulse rate measurements taken in the seated position, and must meet inclusion criteria [6] in order to proceed with dosing (Table HBEH.4). At Visit 3, subjects not fulfilling inclusion criteria [6] at their time 0 BP/pulse rate measurements can have their BP/pulse rate re-evaluated within 3 days. If inclusion criteria [6] is subsequently met (within 3 days of Visit 3), subject may proceed with dosing. If inclusion criteria [6] is subsequently not met (within 3 days of Visit 3), the subject must be discontinued. Subjects who continue to meet entry criteria will be randomized to LY3154207 (10, 30, or 75 mg QD) or placebo immediately following confirmation that subject meets inclusion criteria [6]. Subjects should be dosed immediately after randomization.

The time 0 mean BP and pulse rate will be used for the baseline measurement to assess the change threshold for the development of potentially clinically significant BP/pulse rate (Table HBEH.3).

After time 0, in-clinic BP and pulse rate measurements will be taken every 60 minutes in the seated position only for up to 8 hours. Subjects who meet potentially clinically significant BP/pulse rate measurement (Table HBEH.3) at 3 consecutive timepoints (Day 1 stopping rules) should be discontinued from the study.

Table HBEH.3. Potentially Clinically Significant Vital Sign Criteria

	Low^a	High^a
Systolic BP (mm Hg)	≤90 AND ≥20 decrease	≥180 AND ≥20 increase
Diastolic BP (mm Hg)	≤50 AND ≥15 decrease	≥105 AND ≥15 increase
Pulse Rate (bpm)	≤50 AND ≥15 decrease	≥120 AND ≥15 increase
Abbreviations: BP = blood pressure, bpm = beats per minute, mm Hg = millimeters of mercury		
^a Both conditions on absolute AND relative values are required for the measures to meet the criteria for potentially clinically significant (for example BP ≥180 AND ≥20 increase are both required for systolic blood pressure to meet the criteria for potentially clinically significant)		

Table HBEH.4. Vital Sign Inclusion Criteria [6] for Subjects at Visit 1 and Visit 3 (time 0)

	Subjects <60 Years	Subjects ≥60 Years
Mean Systolic BP^a (mm Hg)	≤140	≤150
Mean Diastolic BP (mm Hg)	≤90	≤90
Mean Pulse Rate (bpm)	≤90	≤90

^a Each of the 3 SBP measurement must be less than 180 mmHg

5.1.3.2. PK Sample

A PK sample is to be collected within 1 to 3 hours after the drug is administered at the site. The date and time of the PK sample collection as well as the date and time of the dose administration immediately preceding the PK sampling will be recorded.

5.1.3.3. Home Blood Pressure Monitoring

Home BP measurements should be conducted for a minimum of 7 days between Visit 2 and Visit 3, for approximately 3 weeks between Visit 3 and Visit 6, and for a minimum of 7 days between Visit 10 and Visit 11, and Visit 11 and Visit 801. Home BP should be measured twice in the morning (approximately 1 minute apart) (e.g., 8 AM) immediately following study medication dosing and twice in the evening, approximately 12 hours later (approximately 1 minute apart) (e.g., 8 PM).

5.1.3.4. Visit 4 to Visit 11

Visits will occur at weekly intervals (7 days \pm 1 day) for Visit 4 through Visit 7, and will occur at biweekly intervals (14 days \pm 3 days) for Visit 8 through Visit 11.

Study drug is to be administered at the clinic on the morning of Visit 8 and Visit 11 following the Time 0 in-clinic BP/pulse rate measurements.

In-clinic BP/pulse rate monitoring at Visit 8 and Visit 11 will be conducted as described in Section 5.1.2.

At each visit, the CDR-CCB should be assessed after the study drug has been administered. At Visit 4, Visit 5, Visit 6, Visit 7, Visit 9, and Visit 10, if a subject has not taken study drug prior to the study visit, the subject must take study drug at the site prior to the CDR-CCB assessment.

MoCA, ADAS-Cog13, MDS-UPDRS [Part III], and D-KEFS will be performed according to the Study Schedule.

Caregiver's inputs will be needed at Visit 4, Visit 8, Visit 11, or ET/ DC for the PDAQ-15, Alzheimer's Disease Cooperative Study – Clinician Global Impression of Change (ADCS-CGIC), MDS-UPDRS, NPI, ESS, GDS-S, and/or QUIP scales. Caregiver's input, separate from the subject, will be needed at Visit 11, Visit 111 and Visit 801 for the PWC-20 early termination.

5.1.4. Telephone Visit (Visit 111)

A telephone visit will be conducted 2 days following Visit 11. The PWC-20 will be assessed with the subject and caregiver, separately, at this telephone visit.

5.1.5. Follow-Up Period (Visit 801)

A follow-up visit will be performed at Visit 801, which will occur 14 days \pm 3 days following the subject's last dose of study medication.

Visit 801 is expected to be of a duration of approximately 2 hours.

Caregiver's inputs will be needed at Visit 801 for MDS-UPDRS, PWC-20, and ESS.

See the Schedule of Activities (Section 2) for the timing of events and the measures to be assessed during the follow-up period.

5.2. Number of Subjects

Approximately 750 subjects will be screened to achieve 340 randomized and evaluable subjects for an estimated total of 85 evaluable subjects per treatment group.

5.3. End of Study Definition

End of the study is the date of the last scheduled procedure shown in the Schedule of Activities (Section 2) for the last subject.

5.4. Scientific Rationale for Study Design

Study HBEH will include subjects who meet the revised MDS criteria for PD (Postuma et al. 2015) or those who meet the revised criteria for DLB, and all who have mild-to-moderate dementia as defined by a decline in cognitive function, which in the opinion of the investigator has resulted in functional impairment and a MoCA score between 10 and 23 (Trzepacz et al. 2015). The inclusion of LBD (PDD or DLB) in HBEH meets current thinking about LBD that, apart from the timing of cognitive impairment, PDD and DLB are clinically and pathologically indistinguishable and would likely respond to similar therapeutic approaches (Aarsland et al. 2004; Ballard et al. 2006).

Placebo is included as the control, in a blinded manner for investigator and site staff and subjects, to allow for an unbiased assessment of the safety data generated, which will allow for a more robust comparison between LY3154207 and placebo data. Comparison of 3 dosage levels of LY3154207 was chosen to evaluate dosage exposure response for safety and efficacy. Initial visits (Visit 3 to Visit 7) were selected to occur at a weekly interval to provide a detailed evaluation of the efficacy and safety of LY3154207 during the initial treatment. A dosing duration of 12 weeks was selected, as it is estimated to be the minimum duration in which a beneficial effect on cognition may be observed.

5.5. Justification for Dose

Three fixed dosages of LY3154207 (10, 30, or 75 mg administered orally [or 50 mg QD, see Section 10.3.7, Interim Analysis]) were selected based on current preclinical pharmacology and toxicology data, and clinical PK, pharmacodynamic and safety data.

The key considerations regarding the dose selection were to:

- ensure a broad exposure exploration around the effective concentration 25 (EC25) defined as the drug concentration at which 25% of the maximal response has been achieved. CCI [REDACTED]
- CCI [REDACTED]
- explore the possibility of an inverted U-shaped pharmacodynamic effect on cognition
- explore whether different dosages of LY3154207 have differential efficacy on domains of PD (cognition, motor, wakefulness).

In Study HBEA, CSF samples were collected in healthy subjects, and the peak mean CSF concentrations of LY3154207 following a CCI [REDACTED]

[REDACTED] Given that LY3154207 PK is dose linear, the proposed dosages of 10, 30, and 75 mg LY3154207 are expected to encompass CCI [REDACTED]

CCI [REDACTED]

CCI

Evidence from D1 agonists and other activating agents working via dopamine pathways suggests an inverted U-shaped pharmacodynamics effect on cognition (Cools and D'Esposito 2011).

Although there is no evidence of an inverted U-shaped response in the Phase 1 data, CCI

CCI

in sleep-deprived healthy subjects receiving a single dose of LY3154207.

Taken together, these data suggest that a CCI is likely to cover a broad exposure range, will allow exploration of the broad range of pharmacodynamic effects, may identify an inverted U-shaped dose–response relationship if such effect exists, minimize the risk of either under- or overdosing, and explore differential effects on relevant clinical domains (cognition, motor, wakefulness).

6. Study Population

Prospective approval of protocol deviations to recruitment and enrollment criteria, also known as protocol waivers or exemptions, are not permitted.

6.1. Inclusion Criteria

Subjects are eligible to be included in the study only if they meet all of the following criteria (note that inclusion criteria [6] must be met at additional visits):

Type of Subject and Disease Characteristics

- [1] Male and female subjects aged 40 to 85 years (inclusive).
- [45] Meet diagnostic criteria for PD (Postuma et al. 2015) or DLB (McKeith et al. 2017) (See [Appendix 5](#) and [6](#))
- [2] Inclusion criterion 2 removed with Amendment b
- [3] Have dementia as defined by a decline in cognitive function, which in the opinion of the investigator has resulted in functional impairment.
- [4] Have a MoCA score of 10 to 23
- [5] Are Modified Hoehn and Yahr Stages 0 to 4.
- [6] Have a BP or pulse rate at Visit 1 and Visit 3 (time 0), as determined by 3 sequential BP/pulse rate measurements in the seated position:
 - Subjects <60 years old:
 - a mean systolic blood pressure (SBP) less than or equal to 140 mmHg, a mean diastolic BP less than or equal to 90 mmHg, and a mean pulse rate less than or equal to 90 beats/min in the seated position.
 - each of the 3 SBP measurement must be less than 180 mmHg.
 - Subjects \geq 60 years old:
 - a mean SBP less than or equal to 150 mmHg, a mean diastolic BP less than or equal to 90 mmHg, and a mean pulse rate less than or equal to 90 beats/min in the seated position.
 - each of the 3 SBP measurement must be less than 180 mmHg.
- [7] If on anti-parkinsonian agents, subjects must be on stable dosage for at least 3 weeks prior to Visit 1, and should remain on stable doses during the course of the study.
- [8] If on medications affecting cognition (rivastigmine, galantamine, donepezil, memantine), subjects must be on stable dosage for at least 3 weeks prior to Visit 1 and should remain at a stable dosage during the course of the study.

- [9] If on antidepressant medications, subjects must be on stable dosage for at least 3 weeks prior to Visit 1 and should remain at a stable dosage during the course of the study.
- [10] If on clozapine, quetiapine, and pimavanserin to address drug-induced or disease-related psychosis, subjects must be on stable dosage for 3 weeks prior to Visit 1 and should remain at a stable dosage during the course of the study.
- [11] If on antihypertensive medications, subjects must be on stable dosage for at least 3 weeks prior to Visit 1

Subject Characteristics

- [12] Contraception.
- [12a] Male subjects, regardless of their fertility status, with nonpregnant WOCBP partners must agree to either remain abstinent (if this is their preferred and usual lifestyle) or use condoms as well as 1 additional highly effective (less than 1% failure rate) method of contraception (such as combination oral contraceptives, implanted contraceptives, or intrauterine devices) or effective method of contraception (such as diaphragms with spermicide or cervical sponges) for the duration of the study and until their plasma concentrations are below the level that could result in a relevant potential exposure to a possible fetus, predicted to be 90 days following the last dose of study drug (below the no-observed-adverse-effect-level [NOAEL]/10) plus 90 days.
- [12b] Men and their partners may choose to use a double-barrier method of contraception. (Barrier protection methods without concomitant use of a spermicide are not an effective or acceptable method of contraception. Thus, each barrier method must include use of a spermicide. It should be noted, however, that the use of male and female condoms as a double barrier method is not considered acceptable due to the high failure rate when these barrier methods are combined).
- [12c] Men with pregnant partners should use condoms during intercourse for the duration of the study and until 93 days following the last dose of study drug.
- [12d] Men should refrain from sperm donation for the duration of the study and until their plasma concentrations are below the level that could result in a relevant potential exposure to a possible fetus, predicted to be 93 days following the last dose of study drug.
- [12e] Female subjects not of childbearing potential may participate and include those who are:
- infertile due to surgical sterilization (hysterectomy, bilateral oophorectomy, or tubal ligation), congenital anomaly such as Mullerian agenesis; or

- post-menopausal – defined as:
 - A woman at least 40 years of age with an intact uterus, not on hormone therapy, who has had at least 1 year of spontaneous amenorrhea with a follicle-stimulating hormone level >40 mIU/mL; or
 - A woman 55 or older not on hormone therapy, who has had at least 6 months of spontaneous amenorrhea; or
 - A woman at least 55 years of age with a diagnosis of menopause prior to start of hormone replacement therapy.

[13] In the investigator's opinion is able to comply with all appointments for clinic visits, tests, and procedures, including venipuncture, computerized assessments and examinations required by the protocol.

[14] Are able to swallow capsules.

[15] Have a level of understanding such that the subject can communicate with the site study personnel, understand the study requirements.

[16] All subjects must have a reliable caregiver who is in frequent contact with the subject (defined as at least 10 hours per week) and will accompany the subject to Visit 1, Visit 2, Visit 4, Visit 8, Visit 11, Visit 111 (telephone only) and Visit 801.

[17] The caregiver must be able to communicate with site personnel and be willing to comply with protocol requirements, and in the investigator's opinion must have adequate literacy to complete the protocol-specified questionnaires.

[18] Agree not to post any personal medical data related to the study or information related to the study on any website or social media site (e.g., Facebook, Twitter, LinkedIn, Google+, etc.).

Informed Consent

[19] Provision of signed and dated informed consent form (ICF) from subject and caregiver prior to any study-specific procedures being performed.

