6.3. Lifestyle Restrictions

Subjects should be instructed not to donate blood or blood products during the study or for 93 days following the last dose of LY3154207. Male subjects should be instructed to not donate sperm during the study for 93 days following the last dose of LY3154207.

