6.1. Inclusion Criteria

Study HBEH will include men and women aged 40 to 85 years with mild to moderate PDD. Subjects are eligible to be included in the study only if they meet all of the following criteria (note that inclusion criteria [6] to [10] must be met ~~or~~ at an additional visits):

Type of Subject and Disease Characteristics

- [1] Male and female subjects aged 40 to 85 years (inclusive).
- [45] Meet diagnostic criteria for PD (Postuma et al. 2015) or DLB (McKeith et al. 2017) (See Appendix 5 and 6 for details)
- [2] ~~Have idiopathic PD per MDS criteria (Postuma et al. 2015) with at least 2 years of PD symptoms.~~
- [5] Are Modified Hoehn and Yahr Stages 1-0 to 4.
- [6] Have a BP or pulse rate at Visit 1 and Visit 3 (time 0), as determined by 3 sequential BP/pulse rate measurements in the seated position:

- [7] If on anti-parkinsonian agents, subjects must be on stable dosage for at least 4 ~~3~~ weeks prior to Visit ~~1~~ 2, and ~~it is anticipated that no changes will be needed~~ should remain on stable doses during the course of the study.
- [8] If on medications affecting cognition (rivastigmine, galantamine, donepezil, memantine), subjects must be on stable dosage for at least ~~8~~ 3 weeks prior to Visit ~~2~~ 1 and ~~expected to~~ should remain at a stable dosage during the course of the study.
- [9] If on antidepressant medications, subjects must be on stable dosage for at least ~~8~~ 3 weeks prior to Visit ~~2~~ 1 and ~~expected to~~ should remain at a stable dosage during the course of the study.
- [10] If on clozapine, quetiapine, and pimavanserin to address drug-induced or disease-related psychosis, subjects must be on stable dosage for ~~3~~ 4 weeks prior to Visit ~~1~~ 2 and expected to remain at a stable dosage during the course of the study.
- [11] If on antihypertensive medications, subjects must be on stable dosage for at least ~~3 months~~ 3 weeks prior to Visit 1.
- [12c] Men with pregnant partners should use condoms during intercourse for the duration of the study and until ~~the end of estimated relevant potential exposure in WOCBP (below the NOAEL/10) plus 90~~ 3 days following the last dose of study drug.
- [12d] Men should refrain from sperm donation for the duration of the study and until their plasma concentrations are below the level that could result in a relevant potential exposure to a possible fetus, predicted to be ~~930~~ 90 days following the last dose of study drug ~~(below the NOAEL/10) plus 90 days~~.

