6.3. Lifestyle Restrictions

Subjects should be instructed not to donate blood or blood products during the study or for 930 days following the last dose (~~below the NOAEL/10~~) ~~plus 90 days of~~ LY3154207. Male subjects should be instructed to not donate sperm during the study for 930 days following the last dose of LY3154207.

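### Inclusion criteria [12a] and [12d] predict different times after the last dose (90 plus 90 days, and 93 days) for the same plasma event, without explanation

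*Protocol*

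**What the plan says.** All of the relevant current text is in the protocol; the SAP does not address it.

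- **Section 6.1, [12a]** (men with nonpregnant partners of childbearing potential). They must agree to abstinence or contraception during the study and "until their plasma concentrations are below the level that could result in a relevant potential exposure to a possible fetus". The criterion then gives the time: "predicted to be 90 days following the last dose of study drug (below the no-observed-adverse-effect-level [NOAEL]/10) plus 90 days".
- **Section 6.1, [12d]** (sperm donation). The same plasma-concentration clause is repeated, and the time is "predicted to be 93 days following the last dose of study drug".
- **Section 6.1, [12c]** (condom use with pregnant partners). The restriction runs "until 93 days following the last dose of study drug". No plasma threshold is named.
- **Section 6.3, Lifestyle Restrictions.** Men are to be "instructed to not donate sperm during the study for 93 days following the last dose of LY3154207". The sentence before it applies 93 days to blood donation by all subjects. Neither sentence names a threshold.

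Agreement to [12a] is a condition of entry for the men it covers, and the opening of Section 6 does not allow waivers of enrollment criteria.

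**The concern.** Contraception and sperm donation could reasonably carry different restriction periods. The difficulty is that [12a] and [12d] do not simply state two periods. Each presents its figure as the predicted time of one event, the same drug falling below a fetal-exposure level in a man's plasma. One event should have one predicted time.

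What is at stake depends on which figure is right:

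- If 93 days is right, [12a] binds men for longer than needed. A man who would accept 93 days but not 180 is ineligible as the criterion is written.
- If 180 days is right, the sperm-donation limits in [12d] and 6.3 are too short, which is the unsafe direction. Section 6.2.1 says that development and reproduction studies have not been conducted.

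Most of the restriction falls after the last scheduled contact. Visit 801 is 14 ± 3 days after the last dose (Section 5.1.5), so adherence depends largely on the instruction given being clear.

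**Working it through.** The check compares current text with current text. No sample-size or power formula applies.

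**Inputs**

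| Place | Restriction | Stated time after last dose | Plasma threshold named? |
|---|---|---|---|
| 6.1 [12a] | Contraception | 90 days plus 90 days | Yes |
| 6.1 [12d] | Sperm donation | 93 days | Yes, same clause |
| 6.1 [12c] | Condoms, pregnant partner | 93 days | No |
| 6.3 | Sperm donation | 93 days | No |
| 6.3 | Blood donation | 93 days | No |

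**Step 1. Read [12a] as a total restriction period.** 90 + 90 = 180 days. Against [12d]: 180 − 93 = 87 days.

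**Step 2. Read only the first component of [12a] as the time to the threshold, with the second 90 days as an added interval.** The threshold is then reached at 90 days in [12a] and at 93 days in [12d]. 93 − 90 = 3 days.

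**Step 3. Compare.** Neither 180 nor 90 equals 93, so no reading of [12a] reproduces the figure in [12d]. A figure could be right as a number and still carry the wrong label, for example if 93 days is a total restriction period worded as a time to threshold. That is why the conclusion is that at least one figure is wrong or mislabelled.

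**Step 4. Look for a stated reason.** No visible text in either document gives a reason for a longer period in [12a]. The absence of reproductive studies (6.2.1) would apply to sperm donation as much as to contraception.

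**Step 5. Time beyond the last visit.** Taking Visit 801 at its nominal 14 days, 93 − 14 = 79 days of the restriction remain under one figure and 180 − 14 = 166 days under the other.

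**The case against.** **The criteria may differ on purpose.** They cover different acts, and [12a] carries a parenthetical reference to one tenth of the no-observed-adverse-effect level that [12d] lacks. The thresholds are therefore not proved identical, and a deliberately wider margin for contraception cannot be excluded, particularly as some rationale text is blacked out. This lowers certainty about the cause. It does not remove the inconsistency, because both criteria use the same fetal-exposure clause and the same form of prediction, and neither says that a different margin is intended.

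**The consequence is slight.** The longer period is the one in [12a], so the criterion errs on the safe side. A man can satisfy every criterion at once. The number of men affected is not given, and the consent form is not available, so actual confusion among participants cannot be shown. All of this stands and fixes the severity.

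**Stronger readings that the documents do not support.**

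- A reader might infer that [12a] was overlooked in amendment (b), because the Appendix 7 mark-up removes similar wording from [12c], [12d] and 6.3 and lists no change to [12a]. That is suggestive only. The log describes superseded text, its digits cannot be read reliably in the available text, and it does not say which figure is right.
- A reader might use the amendment's remark that 2 days is about 5 half-lives to show that 90 days is wrong. At 2 / 5 = 0.4 day per half-life, 90 days is 90 / 0.4 = 225 half-lives, but 93 days is 93 / 0.4 = 232.5. Both look implausible as pure washout, so the argument does not choose between them. It also rests on one approximate phrase, with no concentration or no-effect level given.
- A reader might add that a 3-day washout plus 90 days makes 93. The arithmetic works, but the documents do not state a 3-day washout.

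**Conclusion.** The inconsistency is real and lies in current text. [12a] and [12d] give different predicted times for what is worded as the same plasma event, and at least one is wrong or mislabelled. The difference is 87 days on the total reading of [12a] and 3 days on the time-to-threshold reading.

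This rests on taking the shared clause at face value as one event, and on the absence of any visible reason for a longer period in [12a]. The documents do not settle which period is correct. That 93 days appears everywhere else makes it the more likely intended figure, but does not establish it. Nor do the documents show that any subject or fetus was put at risk.

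Severity is minor. This is an eligibility and fetal-safety figure and should be stated once and correctly, but no endpoint, analysis or sample-size figure depends on it.

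**What to change.** Ask the sponsor to confirm the period, then make one of these changes:

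1. **If 93 days is correct:** change [12a] to 93 days after the last dose, in line with [12c], [12d] and 6.3.
2. **If 180 days is correct:** lengthen [12d] and the sperm-donation sentence in 6.3 to 180 days, and re-check [12c] and the 93-day blood-donation sentence in 6.3.
3. **If [12a] is meant to be longer than [12d]:** say so in [12a] and give the reason in a sentence.

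The cost is a one-line edit in [12a], or short edits to [12d] and 6.3 (and to [12c] if the re-check calls for it), with the consent form checked for the same figure. Design, data collection and analysis do not change.
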